### 1.5 Study rationale

By facilitating loop solving, Endorail should be able to provide several potential benefits, which include fewer attempts at straightening the scope, shorter duration of looping, decreased mean caecal intubation time, higher procedure completion rates, higher diagnostic efficiency, reduced health care costs, reduced stretching forces exerted on the colon walls and attachments, reduced risk of perforation during diagnostic colonoscopy, reduced risk of splenic injury during diagnostic colonoscopy, reduction of the evoked pain and patient discomfort, reduction, and in some cases elimination, of the need for sedation, and reduction of cardiorespiratory complications. All these benefits need to be demonstrated in properly designed clinical trials.

The current study has been conceived considering that Endorail should allow to facilitate colonoscopy completion. Long-lasting colonoscopies represents a challenging subset of patients with higher risk of incomplete colonoscopy. Our study is intended to demonstrate the efficacy and safety of the Endorail in ensuring that incompletion rate, even in long-lasting colonoscopies, is lower than the 10% threshold as recommended by international guidelines.

### 1.6 Explanation for choice of comparator

Caecal intubation rate is an important quality measure in colonoscopy. The completion of the insertion process by fully intubating the cecum allows the endoscopist to perform a complete examination of the colon mucosa upon withdrawal. Caecal intubation is an objective parameter that, according to the standard of care, should be collected during any colonoscopy. International guidelines recommend achieving an incompletion rate lower than 10%. This numerical target value is derived from historical data from clinical studies and may be used as effectiveness endpoint (See Section 1.4).

Adverse events occurrence during colonoscopy is well documented in international literature and can be used as safety endpoint.

Considering the extensive objective data available from literature and the standard of care, we believe that valid scientific evidence to determine whether there is reasonable assurance that the Endorail is safe and effective may come from an objective trial without matched controls.

### 1.7 Risks / Benefits

Patients with long lasting colonoscopy are characterized by high risk of incomplete colonoscopy and adverse events. Indeed if caecal intubation time is longer than 10 minutes, it means that the procedure is more challenging and traumatic and more sedation is required. Endorail has been developed to facilitate colonoscopy completion, thus it can provide a significant benefit to this population.

From a safety perspective, reassuring evidence supports the safety of magnetic devices for endoscopic procedures. Magnets in gastrointestinal endoscopy are involved in applications such as

magnetic maneuverable capsule endoscopy, magnetic foreign body removal, magnetically tracked enteral tube placement, compression anastomosis, magnetic anchoring, magnetic retraction, magnetic sphincter augmentation and magnetic tumor marking [6].

There have been several reports of anchoring technology in humans. Dominguez et al reported no magnet related complications or conversions using neodymium magnetic forceps in 40 patients undergoing laparoscopic cholecystectomy [10]. The Magnetic Surgical System (by Levita Magnetics) is indicated in the U.S. to grasp and retract the body and the fundus of the gallbladder in laparoscopic cholecystectomy and the liver in bariatric procedures to facilitate access and visualization of the surgical site.

PUMA-G System (by CoapTech LLC) is an accessory to enteral feeding tubes that, using the magnetic anchoring of its balloon, enables ultrasound-based placement of percutaneous gastrostomy feeding tubes. In particular the balloon of the device PUMA-G System is filled with a saline solution and the magnetic anchoring force towards the external magnet is ensured by a small magnetic needle hosted within the balloon.

Endorail magnetic balloon anchorage is exerted thanks to the Endorail Ferromagnetic Fluid which is a dispersion of micrometric carbonyl iron particles (CIP) in hypertonic water-based solution containing sodium citrate and sodium chloride. The ferromagnetic fluid contained in the syringe is not intended to be in contact with the patient, however the possibility of a contact has been taken into account. Carbonyl iron particles incorporate excellent biocompatibility and safety factors with their unique magnetic properties; therefore, they have been used in biomedical applications such as oral iron supplements for iron deficiency anemia.

Evidences gathered in literature suggest that carbonyl iron powders possess a low potential for acute systemic toxicity when ingested. This is most likely related to the long solubilization process that they undergo into the stomach. Since such solubilization process does not take place into the large intestine, it is deemed unlikely for a CIP to be readily absorbed by the tissues of this body structure. In the case of the Endorail, it is suggested to take appropriate countermeasures to ensure that accidentally poured CIP is endoscopically removed as much as possible from the patient's large intestine. Indeed CIP is grey and in case of leakage it is very easy to be detected. The endoscopist can use the colonoscope to wash the lumen and remove the iron powder in few minutes. These countermeasures and the low probability of absorption by the tissues of the large intestine are expected to contribute to a very low biological risk for the patient.

The planned clinical investigation will assess the safety and tolerability of Endorail by collecting general adverse events and specific adverse events, such as gastrointestinal bleedings, intestinal perforation, mucosal petechiae and abdominal pain. Overall, there are no expected or unexpected risks or complications that may emerge from the use of the Endorail in the patient population selected in this investigational protocol. Therefore, it is expected that benefits from the participation in this investigation will outweigh the potential risks.

## 1.8 Justification of choice of study population

The study population includes outpatients of both sexes, aged between 22 and 75 years (inclusive), undergoing diagnostic and surveillance colonoscopy, who have signed a written informed consent.

The choice of study population is guided by the need to obtain a homogeneous patients' sample and to collect data that are comparable with those available in the literature, allowing an accurate and unbiased statistical analysis. Moreover, all those conditions that could impair the patient's safety have been excluded.

A population between 22 and 75 years of age has been chosen since the aim is to study the Endorail device in the treatment of adult population; to be compliant with FDA regulation, the age of majority in the United States was used as reference. Moreover, since it is known in the literature that the occurrence of adverse events is greater in the older population, patients aged >75 years are excluded.

Targeting a homogeneous population, the choice to include surveillance and diagnostic colonoscopies is justified by the fact that both refer to comparable guidelines and that the data in the literature are comparable. On the contrary, screening colonoscopies were excluded because they present a different completion rate than the previous two, while therapeutic colonoscopies present a higher risk of occurrence of adverse events.

In conclusion, the population was chosen homogeneously in order to compare it with the data available in literature, to create as few confounding factors as possible and to exclude any conditions that might impact on patient and device safety.

## 2. STUDY OBJECTIVES

The aim of this study is to test the safety and efficacy of Endorail in ensuring low incompleteness rate in long-lasting colonoscopies.

### 2.1 Primary Objective

#### Efficacy (Timeframe: day 1)

To validate the efficacy of Endorail in long-lasting colonoscopies by reaching a colonoscopy incompleteness rate minor or equal to 10%.

AND

#### Safety (Timeframe: day 1 to day 7)

To validate the safety of Endorail in long-lasting, colonoscopies by demonstrating that colonoscopy serious adverse events are not increased using the device (i.e., in particular the absence of device-related serious adverse events).

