Endpoint(s)	
Efficacy:
 
The primary efficacy endpoint is the percentage minor or equal to 10% of incomplete long-lasting colonoscopies (colonoscopy is defined completed when caecal intubation is achieved)
 
AND
 
Safety:
 
Medical adverse events and medical device adverse events will be collected during the study. The primary safety endpoints are:
 
The absence of device-related serious adverse events.
 
AND
 
The evaluation of the equality or reduction of the adverse events rates compared to colonoscopies without Endorail.
 
The adverse events assessed are:
 
 
• Occurrence of general adverse events and medical device incidents;
 
• Occurrence of specific adverse events: gastrointestinal bleedings, intestinal perforation, mucosal petechiae and abdominal pain.
 

Study design:	Multi Centre, Post Market, Single-Arm, Open-Label, Interventional Study

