#### 1.2.3 Long lasting colonoscopy

A colonoscopy can be defined as difficult or long-lasting when caecal intubation time is longer than 10 minutes. Long lasting colonoscopies are cause of stress and delays in the workflow. Moreover, longer procedures are characterized by more traumatic manoeuvres, increased pain and discomfort, higher sedation requirements and higher risk of severe complications such as cardiorespiratory events and bowel perforation.

As data from literature shows that about 80% of all diagnostic colonoscopies are typically completed in less than 10 minutes, the long-lasting colonoscopy subset represents approx. 20% of the total procedures. Indeed, since nearly virtually all incomplete colonoscopies are also long-lasting, the risk of incompleteness in this subset of patients increases nearly five-fold (i.e., for a 5x increase, the lower bound of the rate increases from 4% to 20%) [1][7][17][20].

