### 1.2.4 Complications in colonoscopy

Severe complications such as cardiorespiratory events and bowel perforation, although rare, can develop during colonoscopy [10]. Serious gastrointestinal events; myocardial infarction; stroke; pneumonia occurrence rates in screening or surveillance colonoscopy are 47 persons, 4 persons, 7 persons and 10 persons per 100'000, respectively [30].

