## 3. STUDY ENDPOINTS

### 3.1 Primary Endpoints:

Efficacy:

The primary efficacy endpoint is the percentage minor or equal to 10% of incomplete long-lasting colonoscopies (colonoscopy is defined completed when caecal intubation is achieved)

AND

Safety:

Medical adverse events and medical device adverse events will be collected during the study.

The primary safety endpoints are:

The absence of device-related serious adverse events.

AND

The evaluation of the equality or reduction of the adverse events rates compared to diagnostic colonoscopies without Endorail.

The adverse events assessed are:

- Occurrence of general adverse events and medical device incidents;
- Occurrence of specific adverse events: gastrointestinal bleedings, intestinal perforation, mucosal petechiae and abdominal pain.

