#### **5.2.2 Control Intervention (Clinical Practice)**

This clinical trial has no prospective control group; results about primary endpoints for efficacy and safety will be compared with the standard clinical practice and international guidelines reference values (Section 1.6).

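### A single-arm trial of 38 to 95 patients cannot show that serious adverse events are not increased, and the broader adverse-event comparison has no reference rate

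*Combined protocol and SAP*

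**What the plan says.** Section 2.1 and the synopsis make safety a primary objective, joined by AND to efficacy, to be met "by demonstrating that colonoscopy serious adverse events are not increased using the device (i.e., in particular the absence of device-related serious adverse events"). Section 3.1 turns this into two primary safety endpoints, also joined by AND. The first is "The absence of device-related serious adverse events". The second is "The evaluation of the equality or reduction of the adverse events rates compared to diagnostic colonoscopies without Endorail"; the synopsis has "The evaluation of the equality or reduction of the adverse events rates compared to colonoscopies without Endorail". The events assessed are general adverse events, device incidents, and four specific events: gastrointestinal bleeding, perforation, mucosal petechiae and abdominal pain.

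There is no concurrent control. Section 5.2.2 says that the efficacy and safety results "will be compared with the standard clinical practice and international guidelines reference values (Section 1.6"). On safety, Section 1.6 says only: "Adverse events occurrence during colonoscopy is well documented in international literature and can be used as safety endpoint". It gives no rate. The one set of figures is in Section 1.2.4, repeated in Section 8.2, for serious gastrointestinal events, myocardial infarction, stroke and pneumonia: "pneumonia occurrence rates in screening or surveillance colonoscopy are 47 persons, 4 persons, 7 persons and 10 persons per" 100,000. Section 8.2 sums them to 0.068%.

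The only hypothesis test (Sections 8.1, 8.2 and 8.4) is a one-sided exact binomial test of a merged indicator, incomplete procedure or adverse event, against 20%. Adverse events are otherwise tabulated and described. Sections 4.6, 8.3 and 8.4.2 allow the trial to end at 38 or 57 patients if that test is significant.

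**The concern.** Claiming that SAEs are not increased is a comparative claim about a rare event. It needs a reference rate for a comparable population, a statement of how large an increase must be excluded, and enough patients to exclude it. The plan gives none of these for safety. Its one reference rate comes from screening or surveillance colonoscopy. Screening is excluded from this trial, and Section 1.2.3 says that long-lasting procedures carry a "higher risk of severe complications such as cardiorespiratory events and bowel perforation".

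Followed as written, the trial could report the primary safety objective as met because few or no SAEs were seen, or because the merged indicator was significant. Neither result would show it, least of all after an early stop at 38 or 57 patients.

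**Working it through.** **Inputs.** Reference rates of 47, 4, 7 and 10 per 100,000 (Sections 1.2.4 and 8.2). Expected incompletion of about 10%, threshold 20%, one-sided alpha 5%, assumed outcome 10.1%, 85 evaluable and 95 enrolled (Section 8.2). Interim looks at 38 and 57 (Section 8.4.2). Exact binomial test (Section 8.4).

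**1. The plan's own figures.**
- Reference rate: (47 + 4 + 7 + 10)/100,000 = 0.068%.
- Merged indicator, taking SAEs as independent of 10% incompletion: 1 − 0.90 × (1 − 0.00068) = 10.06%, the plan's 10.1%.
- Sample size by normal approximation: [(1.645 × √(0.20 × 0.80) + 0.842 × √(0.101 × 0.899)) / (0.20 − 0.101)]² = 84.8, so 85; then 85/0.90 = 94.4, so 95.

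The figures reproduce. They size the merged test only; no sample size is given for safety alone.

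**2. What zero SAEs would show.** The exact one-sided 95% upper limit with no events is 1 − 0.05^(1/n). The expected count at the reference rate is n × 0.00068. The last column takes an illustrative true rate of ten times the reference (0.68%): P(no SAE) = (1 − 0.0068)^n.

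| n | Expected SAEs | Upper limit, 0 events | Multiple of 0.068% | P(0 SAEs) at 0.68% |
|---|---|---|---|---|
| 38 | 0.026 | 7.6% | 111 | 77% |
| 57 | 0.039 | 5.1% | 75 | 68% |
| 85 | 0.058 | 3.5% | 51 | 56% |
| 95 | 0.065 | 3.1% | 46 | 52% |

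Even excluding a tenfold rate takes at least 440 patients with no event: ln(0.05)/ln(1 − 0.0068) = 439.05, rounded up. With 80% power when the true rate is 0.068%, it takes about 700. The tenfold margin is an assumption; the plan names none.

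**3. Whether the merged indicator fills the gap.** The largest count c at which the exact test rejects satisfies P(X ≤ c | n, 0.20) ≤ 0.05.

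| n | c | P(X ≤ c) at 20% | Event rate at c |
|---|---|---|---|
| 38 | 3 | 0.039 | 7.9% |
| 57 | 6 | 0.045 | 10.5% |
| 85 | 10 | 0.033 | 11.8% |
| 95 | 12 | 0.042 | 12.6% |

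If every colonoscopy were completed, all of these events could be SAEs and the test would still be significant, at more than 100 times 0.068%. In the planned setting the indicator barely reacts to SAEs. A tenfold SAE rate moves it from 10.06% to 1 − 0.90 × (1 − 0.0068) = 10.61%. The chance of significance falls only from 77% to 71% at n = 85, and from 84% to 79% at n = 95 (single look, interim looks ignored).

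**4. The broader adverse-event endpoint.** Section 3.1 asks for equal or lower adverse event rates. Section 5.2.2 sends the reader to Section 1.6, which has no rate. The 0.068% covers four serious classes combined. It gives no rate for all adverse events, none for petechiae or abdominal pain, and none for bleeding or perforation individually. The comparison has nothing on its other side.

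**5. A separate wording point.** Sections 8.1 and 8.4.2 count a serious adverse event in the indicator; Section 8.2 counts an adverse event. Only the serious reading fits the 0.068% and 10.1% in Section 8.2.

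**The case against.** **The objective is narrower than it looks.** It singles out the absence of device-related SAEs, and Section 3.1 speaks of evaluating, not demonstrating, equality or reduction. The zero-count criterion can indeed be checked and should stay. But it is given as a particular case of the objective, which still sets out to demonstrate no increase, and the comparative endpoint stands beside it as primary.

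**Detail is deferred.** Section 8.4 leaves detail to a statistical analysis plan finalised before database lock. Confidence limits could be added there. It cannot supply information that 38 to 95 patients do not contain, and the claim sits in the protocol.

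**Safety is formally tested.** SAEs do enter the merged indicator, so it would be wrong to call safety wholly untested. However, Section 8.4 describes that test as proof of efficacy, and its threshold comes from incompletion.

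**The benchmark is strict.** If long-lasting procedures carry more risk, 0.068% is probably too low for this population and works against the device. That is fair. It makes the rate unsuitable as a comparator without rescuing the claim.

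**The criterion is device-related SAEs, not all SAEs.** If only the assumed excess (9 × 0.068%) were device-related, the chance of seeing none would be 79%, 70%, 59% and 56% at 38, 57, 85 and 95 patients. The message is the same.

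**A stronger inference.** A reader might conclude that the sample is too small for every adverse-event comparison. The documents do not support that. For a common event such as abdominal pain, 95 patients may be informative: at an assumed 20% (19/95; the documents give no rate) the exact one-sided 95% upper limit is 28%. There the defect is the missing reference rate. Nor does the looser wording in Section 8.2 show that the sample size is wrong, since that section's own figures fit only serious events.

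**Conclusion.** The concern holds in two distinct parts. For SAEs, the design cannot support a claim of no increase: the best possible result, zero events, leaves rates up to 7.6% (n = 38) or 3.1% (n = 95) compatible with the data, about 111 to 46 times the only reference rate. Significance of the merged indicator does not change this. For adverse events more broadly, equality or reduction cannot be evaluated as written because no reference rate is given; a sample-size shortfall is not shown there.

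The upper limits assume only independent patients, with all of them observed for the event. The multiples rest on 0.068%, which comes from a different mix of patients. The tenfold rate is illustrative, and the indicator calculations assume that SAEs and incompletion are independent. The efficacy test is not affected. The inconsistency between Section 8.2 and Sections 8.1 and 8.4.2 is minor.

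**What to change.** Before the first interim look:

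1. In the synopsis and Sections 2.1 and 3.1, replace the comparative wording with the number and proportion of patients with any SAE, with a device-related SAE and with each specific adverse event, each with an exact one-sided 95% upper limit. State the nominal zero-event limits: 7.6%, 5.1%, 3.5% and 3.1% at 38, 57, 85 and 95 patients.
2. Use all patients who started treatment with Endorail as denominator. For events to day 7, also give the limit among those who completed Visit 2, so that patients lost to follow-up, including those replaced under Section 4.7, are not silently counted as event-free.
3. Keep the absence of device-related SAEs as a separate criterion, and state that meeting it does not show that SAEs are not increased.
4. Align Sections 1.6, 4.1 and 5.2.2 so that literature adverse-event rates, including 0.068% with its four event types and source population, are descriptive context only.
5. State in Section 8.4 that significance of the merged indicator is not evidence of safety. In Section 8.2 write serious adverse event, and say whether it means any SAE as defined in Section 7.1.1 or only the four classes.

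Setting a numeric margin or performance goal is the other route, but at these sample sizes it could exclude only very large increases in SAEs. The cost of the proposed change is a protocol amendment with the written approval that Section 9.5.1 requires, and the loss of a comparative claim that the data cannot carry. No extra patients are needed. Adverse-event counts and proportions are already planned, and the merged indicator and sample size are unchanged.

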## 3. STUDY ENDPOINTS

### 3.1 Primary Endpoints:

Efficacy:

The primary efficacy endpoint is the percentage minor or equal to 10% of incomplete long-lasting colonoscopies (colonoscopy is defined completed when caecal intubation is achieved)

AND

Safety:

Medical adverse events and medical device adverse events will be collected during the study.

The primary safety endpoints are:

The absence of device-related serious adverse events.

AND

The evaluation of the equality or reduction of the adverse events rates compared to diagnostic colonoscopies without Endorail.

The adverse events assessed are:

- Occurrence of general adverse events and medical device incidents;
- Occurrence of specific adverse events: gastrointestinal bleedings, intestinal perforation, mucosal petechiae and abdominal pain.

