## STUDY SYNOPSIS

Sponsor	Endostart s.r.l., [name]
Study Title	Multicenter clinical trial for the evaluation of safety and effectiveness of Endorail in patients with long-lasting colonoscopy
Study Acronym	Endorail
Protocol Version and Date:	V1.1 Date: 24 th October 2022
Clinical Phase:	Post-market
Background and Rationale:	
This clinical trial is intended to expand the clinical knowledge base about safety and efficacy of Endorail in facilitating colonoscopy completion in patients with long lasting colonoscopy.
 
Reported incomplete colonoscopy rates range from 4% to 25%. While international guidelines recommend a rate of less than 10% for diagnostic colonoscopies, the risk is at least 20% in the more challenging subset of patients characterized by long-lasting procedures.
 
A colonoscopy can be defined as “long-lasting” when caecal intubation time is longer than 10 minutes. As data from literature shows that about 80% of all diagnostic colonoscopies are typically completed in less than 10 minutes, the long-lasting colonoscopy subset represents approx. 20% of the total procedures. Indeed, since nearly virtually all incomplete colonoscopies are also long-lasting, the risk of incompleteness in this subset of patients increases nearly five-fold (i.e., for a 5x increase, the lower bound of the rate increases from 4% to 20%) [1].
 
Endorail is intended to facilitate the positioning of a standard colonoscope. One of the main advantages of this device is that it can be used “as needed” during the procedure to prevent incomplete procedures without requiring any “preloading” ahead of time. This makes Endorail particularly indicated for patients in which caecal intubation time gets longer and the risk of incompleteness increases.

Objective(s):	
Primary Objectives:
 
Efficacy (Timeframe: day 1): To validate the efficacy of Endorail in long-lasting colonoscopies by reaching a colonoscopy incompletion rate minor or equal to 10%.
 
AND
 
Safety (Timeframe: day 1 to day 7): To validate the safety of Endorail in long-lasting colonoscopies by demonstrating that colonoscopy serious adverse events are not increased using the device (i.e., in particular the absence of device-related serious adverse events).

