## 8. STATISTICAL METHODS

### 8.1 Hypothesis

This study is designed to test the null hypothesis that the proportion of 'event' (intended as procedure incomplete or serious adverse event) is equal or greater than 20%. The alternative hypothesis is that the proportion of 'event' is less than 20%. In statistical terms:

$$H0: p \geq 20\%$$

$$H1: p < 20\%$$

Where:

$p$  = true proportion of patients with event

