### 8.2 Determination of Sample Size

Efficacy (first primary objective) will be assessed by measuring the colonoscopy completion rate in long-lasting procedures, which is a measurable parameter of clinical value recognized by international medical societies. Safety (second primary objective) will be assessed by measuring the rare of adverse events. They are classified into: serious gastrointestinal events; myocardial infarction; stroke; pneumonia. Based on the literature [30]; their occurrence rates in screening or surveillance colonoscopy are 47 persons, 4 persons, 7 persons and 10 persons per 100'000, respectively.

These two objectives are merged in one indicator, which is equal to 1 for each subject if the procedure is incomplete or an adverse event occurs, and 0 otherwise.

The non-completion rate of long-lasting colonoscopies conducted with Endorail is expected to be around 10%. This will be compared to the above-mentioned threshold of 20% for incomplete procedures. It should be noted that this threshold is conservative and represents the most critical setting for comparison with respect to the state of the art, as it is derived from the lower bound of the range from the literature.

When including the safety to provide the expected value of the indicator for Endorail and the corresponding threshold, the above values of 10% minimally change, as the adverse event

occurrence rate is 0.068% (given by the sum of the occurrence of the 4 events reported above per 100'000 persons, expressed in percentage).

With a significance level  $\alpha$  of 5%, assuming a proportion of outcome of 10.1%, 85 patients allow to test with a power of 80% the  $H_0: p \geq 20\%$  vs  $H_1: p < 20\%$ , where 20% is the estimated percentage of incomplete procedure from literature.

The chosen number is then increased by the 10% to account for possible drop-out (e.g., cases to be discarded, losses to follow-up, etc.), resulting in  $85/0.90 = 95$  patients to be actually enrolled.

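### The endpoint sets efficacy success at 10% incompletion or less, but the only test, the 80% power and the stopping rule concern 20% on a composite, and nothing says which decides.

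*Combined protocol and SAP*

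**What the plan says.** **The 10% criterion.** The synopsis says efficacy is validated "by reaching a colonoscopy incompletion rate minor or equal to 10" per cent. Section 2.1 repeats this ("by reaching a colonoscopy incompleteness rate minor or equal to 10" per cent), and section 3.1 writes the figure into the endpoint: "The primary efficacy endpoint is the percentage minor or equal to 10% of incomplete long-lasting colonoscopies". Sections 1.2.6 and 1.5 say the study is meant to demonstrate a rate below the guideline 10%. Section 1.6 says of the guideline figure: "This numerical target value is derived from historical data from clinical studies and may be used as effectiveness endpoint". Section 5.2.2 adds that "results about primary endpoints for efficacy and safety will be compared with the standard clinical practice and international guidelines reference values"; it refers to section 1.6 but gives no figure itself.

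**The 20% criterion.** In section 8.1 the null hypothesis is that the proportion of events is at least 20% ("intended as procedure incomplete or serious adverse event) is equal or greater than 20" per cent). Section 8.2 merges efficacy and safety into one indicator, "equal to 1 for each subject if the procedure is incomplete or an adverse event occurs", and sizes the trial on it: "assuming a proportion of outcome of 10.1%, 85 patients allow to test with a power of 80" per cent. Section 8.4 plans one exact, one-tailed binomial test of that indicator and treats it as the proof of efficacy. Sections 4.6, 8.3 and 8.4.2 allow the trial to end at 38 or 57 patients if that test is significant, with no mention of 10%.

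**The link.** There is none. In section 8.2, 10% appears only as the expected rate. Section 8.4 defers technical detail to an analysis plan due before database lock. The text in hand does not settle which criterion governs.

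**The concern.** A trial run exactly as written could be reported as having proved efficacy under section 8, or could stop at 57 patients, while its observed incompletion rate is above the level that sections 2.1 and 3.1 set for success. A significant result supports only the statement that the rate is below 20%, yet the rationale promises a rate below 10%. The 80% power describes the chance of passing the 20% test and not the chance of meeting the written endpoint. In an open-label single-arm trial, a choice between the two criteria made after data have been seen would be post hoc.

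**Working it through.** **Inputs.** From section 8.2: null value 20%, planned rate 10.1%, one-sided 5%, 85 evaluable and 95 enrolled patients, adverse-event rate 0.068%. From section 8.4: exact binomial test. From section 8.4.2: looks at 38 and 57. From section 3.1: 10% or less. The composite is treated as incompletion alone, since the plan adds only 0.068% for safety. Each look uses the full 5%, because no adjustment is stated.

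**1. The plan's own figure.** n = [1.645·√(0.20·0.80) + 0.842·√(0.101·0.899)]² / (0.20 − 0.101)² = 84.8, so 85. Then 85/0.90 = 94.4, so 95. Both reproduce. They come from the normal approximation; the exact test has 76.3% power at 85 and 84.0% at 95.

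**2. Count limits.** For the test, take the largest c with P(X ≤ c | n, 0.20) ≤ 0.05. For the endpoint, take the largest k with k/n ≤ 0.10.

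| n | Test passes up to | p-value there | One-sided 95% upper limit | 10% or less up to | Counts that pass the test and miss 10% |
|---|---|---|---|---|---|
| 38 | 3 (7.9%) | 0.039 | 19.2% | 3 | none |
| 57 | 6 (10.5%) | 0.045 | 19.7% | 5 | 6 |
| 85 | 10 (11.8%) | 0.033 | 19.1% | 8 | 9, 10 |
| 95 | 12 (12.6%) | 0.042 | 19.7% | 9 | 10, 11, 12 |

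At these four sizes an observed rate of 10% or less always passes the test, because k never exceeds c.

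**3. One fixed-n analysis at a true rate of 10.1%.**

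| Final n | P(observed ≤ 10%) | P(significant) | P(significant, above 10%) |
|---|---|---|---|
| 85 | P(X ≤ 8) = 0.507 | P(X ≤ 10) = 0.763 | 0.763 − 0.507 = 0.255 before rounding of terms, about 26% |
| 95 | P(X ≤ 9) = 0.505 | P(X ≤ 12) = 0.840 | 0.334, about 33% |

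**4. With the two looks, stopping whenever the test is significant, at 10.1%.** The trial stops at 38 with probability 0.457, always at 10% or less. It first stops at 57 with probability 0.106 (5 or fewer incompletions) plus 0.116 (exactly 6).
- Final n = 85: significant at 10% or less is 0.457 + 0.106 + 0.029 = 0.592; significant above 10% is 0.116 + 0.105 = 0.221.
- Final n = 95: the same sums are 0.457 + 0.106 + 0.038 = 0.601 and 0.116 + 0.152 = 0.268.

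**5. Requiring both criteria at every look (limits 3/38, 5/57, then 8/85 or 9/95).** The probability of success at 10.1% is 0.457 + 0.106 + 0.081 = 0.644 (final 85) or 0.457 + 0.106 + 0.091 = 0.654 (final 95).

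**6. The opposite disagreement (10% met, test missed), n = 85, true incompletion 10%.** At the plan's 0.068% event rate the chance is about 0.0003%. If 2% or 5% of completers had a counted adverse event (assumed rates, not in the documents), it would be 4% or 24%. This matters only if any adverse event counts. Sections 8.1 and 8.4.2 say serious adverse event; the indicator in section 8.2 says only an adverse event.

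**The case against.** The strongest reply is that 10% is the planning value and 20% the performance threshold, which is a valid single-arm design with a sample size that reproduces. That stands for section 8.2. It does not cover sections 2.1 and 3.1, which make 10% the level at which efficacy is validated.

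A second reply is that a success chance near one half is no surprise, because any observed-rate target set at the expected rate is met about half the time. This also stands. At n = 85 the target would be met 86% of the time at a true rate of 7% and 97% at 5%. The 51% is therefore not evidence of a poorly sized test. It shows that the stated power does not transfer to the written endpoint.

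Some stronger readings are tempting but not supported:
- **That 51% is the plan's chance of meeting its endpoint.** It applies to one fixed-n analysis only. The permitted looks change it, as steps 4 and 5 show.
- **That the whole stopping rule is compromised.** At 38 patients the limits coincide. Only the look at 57 is affected, and only by one count, 6/57. Stopping is also permitted and not required.
- **That the two criteria readily disagree in both directions.** At the planned sizes and event rate, the opposite direction is negligible.
- **That section 5.2.2 fixes 10% as the reference.** It names no figure, and standard practice could equally mean the 20% rate. Section 1.6 says only that 10% may be used.

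**Conclusion.** The conflict is real and affects the primary efficacy conclusion. The endpoint asks for 10% or less, while the test, the power and the stopping rule ask for less than 20%, and no rule joins them. At the planned 10.1%, a significant result with an observed rate above 10% has probability 26% or 33% with a single analysis at 85 or 95 patients, and about 22% or 27% if the trial stops at the first significant look. The chance of being significant with an observed rate of 10% or less is 51% in either fixed-n case, or about 59% or 60% with such stopping. These figures assume that the composite equals incompletion alone and that each look uses 5%.

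A reader might infer that the test should be moved to 10%. The documents do not support that: the planned rate of 10.1% lies inside a null of 10% or more, and an exact test of it would reject with probability only 2.3% at 85 (limit 3) or 3.1% at 95 (limit 4). The 20% test can stay. What cannot stay is wording that lets it be read as showing a true rate of 10% or below.

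**What to change.** Before the first interim look, amend the synopsis and sections 1.2.6, 1.5, 2.1, 3.1 and 8, with the stopping text in 4.6, to state one efficacy rule.

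- **Option (a).** Success is rejection of a rate of 20% or more. The 10% becomes the planning value and a descriptive benchmark. Incompletion is reported separately from the composite with an exact confidence interval, and the conclusion is limited to below 20%.
- **Option (b), closest to the present endpoint.** Success is significance against 20% and an observed incompletion rate of 10% or less, both applied at every look on the number actually analysed (for example 5/57, not 6/57). At the planned sizes the 10% limit then binds. The probability of success at 10.1% should be restated as about 51% with fixed n, or about 64% or 65% with the two looks and a final n of 85 or 95.

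Under either option:
- keep the separate primary safety condition of section 3.1, no device-related serious adverse events, as a further requirement;
- state that the 80% power refers only to the 20% threshold;
- remove wording that the trial will demonstrate a true rate of 10% or below;
- make sections 8.1, 8.2 and 8.4.2 agree on whether the indicator counts serious adverse events or any adverse event.

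**Cost.** A protocol amendment with written ethics committee and competent authority approval (section 9.5.1). Option (a) gives a less favourable claim; option (b) gives a lower stated probability of success. Neither needs extra patients or another test.
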